#### 9.7. Limitations of the research methods

- The medical records may not be available for each & every data points provided in the CRF, from the aspect of the clinician or the patient.
- Patients may be lost to follow-up due to the occurrence of AEs, lack of efficacy or other reasons.
- This could be due to censoring events, that is, information on time to outcome event may not available for all study participants. Patient/s in such cases will be marked as "censored" when such information on time to event is not available due to loss to follow-up or non-occurrence of outcome events before the end of the study.
- For such patients (censored because of lost to follow-up due to the occurrence of AEs, lack of efficacy or other reasons), the use of Kaplan-Meier curves will be obtained as estimates of median OS, RFS and time to CR/Cri taking into account patients' attrition.
- The interpretation of data collected retrospectively will be dependent on the completeness and quality of the medical records and the reliability of the abstraction of data from the medical records. However, Source data verification (SDV) will be employed to identify and correct abstraction errors.

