# **3. KEY DEFINITIONS**

Index date: The date of initiation of the first cycle of InO.

**Baseline period**: Period from 6 months before index date to the index date. The closest observation recorded during the baseline period and closest to index date will be used as baseline data (when more than one observations are available).

**CR/CRi rate**: Number of patients who achieve complete remission/complete remission with incomplete hematologic recovery (CR/Cri) divided by the total number of patients completing treatment with InO (defined as patients with a recorded date of discontinuation of InO).

**Complete remission (CR)**: is defined as 5% bone marrow blasts, no evidence of disease in the bone marrow, and recovery of peripheral blood count (platelet count of >  $100 \times 109/L$  and absolute neutrophil count of >  $1 \times 109/L$ ).

**CR with incomplete count recovery (CRi)**: is defined as 5% bone marrow blasts and no evidence of disease in the bone marrow, but with incomplete recovery of peripheral blood count. Minimal residual disease (MRD) will be assessed at each participating institution by multicolor flow cytometry.

**MRD negativity r**ate: Proportion of patients in whom minimal residual disease (MRD)-negative status is observed, among patients in whom MRD negativity status has been assessed, at any time until the end of treatment with InO (defined as the date of recorded discontinuation of InO). OS: Time from index date to death.

**RFS:** Time from index date to the earliest date of the following events: death, progressive disease (including objective progression, relapse from CR/CRi, treatment discontinuation due to global deterioration of health status), or the start of new induction therapy or posttherapy haematopoietic stem cell transplantation (HSCT) without achieving CR/CRi.

**EMD**: Extramedullary disease is the presence of leukemic cell aggregates in the form of solid tumor outside that of bone marrow.i

LBL: lymphoblastic lymphoma, is a clonal hematopoietic stem cell disorder of B or T cell originii

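### Protocol 9.7 presents Kaplan-Meier as handling loss due to AEs or lack of efficacy; it does so only if that loss is unrelated to prognosis, and no rule ranks RFS events above censoring

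*Protocol*

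**What the plan says.** Protocol 9.7 (limitations) gives the expected reasons for attrition: "Patients may be lost to follow-up due to the occurrence of AEs, lack of efficacy or other reasons". Patients are marked as censored "when such information on time to event is not available due to loss to follow-up", or when no event has occurred by the end of the study. For the patients lost, described as "censored because of lost to follow-up due to the occurrence of AEs, lack of efficacy or other reasons", Kaplan-Meier curves are then to supply "estimates of median OS, RFS and time to CR/Cri taking into account patients' attrition".

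Protocol Section 3 defines OS as "Time from index date to death", with no censoring rule. It defines RFS as time to the earliest of several events. These are death; "progressive disease (including objective progression, relapse from CR/CRi, treatment discontinuation due to global deterioration of health status"); and new induction therapy or HSCT begun without CR/CRi.

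The SAP plans Kaplan-Meier curves and restricted mean times for OS, RFS and remission-free time (7.1, 7.2, 7.2.2). It analyses available data without imputation (Section 6). Its appendices add no endpoint definitions (A1.2) and no further methods (A2.1). Neither document plans a sensitivity analysis for loss to follow-up or a table of losses by reason.

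**The concern.** Kaplan-Meier lets the patients still under observation stand in for those who were censored. That is sound for administrative censoring and for loss unrelated to outcome. Loss because the drug failed or was not tolerated is different, because the reason itself carries prognostic information. The protocol's own background (Section 7) lists CR, MRD negativity and subsequent HSCT as predictors of better survival. By that account, patients lost for lack of efficacy come from the poorer-prognosis group. Section 9.7 acknowledges the attrition, but credits the method with a protection that it gives only under an unstated assumption.

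RFS has a second problem. Several sites will abstract paper charts. A chart may say that a patient stopped coming because treatment was not working, or because of decline, and give a last-visit date but no formal progression date. One abstractor could code an event, citing "treatment discontinuation due to global deterioration of health status" or progression. Another could code censoring, citing loss for lack of efficacy. Nothing says which prevails.

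The resulting medians and survival rates are likely to be read beside the phase 3 figures quoted in the background (median OS 7.7 months, median PFS 5.0 months).

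**Working it through.** The documents state no loss rate, no risk after loss and no expected OS or RFS for this cohort, so there is no planned figure to reproduce. The calculations below are illustrations under stated assumptions.

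**1. RFS when non-responders are coded as censored**

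Inputs from the documents:
- 32 patients (administrative change letter to Protocol 9.3).
- Response 81% and median remission 4.6 months (phase 3 InO arm, Protocol Section 7). 32 × 0.19 ≈ 6 non-responders, leaving 26 responders.

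Assumptions: non-responders fail evenly between 1 and 2 months; responders remit at 1.2 months and then relapse exponentially with median 4.6 months.

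- True 6-month RFS = (26/32) × 0.5^((6 − 1.2)/4.6) = 0.8125 × 0.485 = 39.4%.
- True median: 0.8125 × 0.5^((t − 1.2)/4.6) = 0.5 gives t = 1.2 + 4.6 × log2(1.625) = 4.4 months.
- With k of the 6 censored at their failure time, the large-sample Kaplan-Meier curve is exp(−∫ dE/Y), where E counts recorded events only and Y is the share still at risk.

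| k censored | 6-month RFS | Median (months) |
|---|---|---|
| 0 | 39.4% | 4.4 |
| 2 | 42% | 4.9 |
| 4 | 46% | 5.4 |
| 6 | 49% | 5.9 |

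Hand check of the last row: dropping all six from the start leaves the responder curve, 0.5^(4.8/4.6) = 48.5%, with median 1.2 + 4.6 = 5.8 months. The small remainder arises because the six stay in the risk set for part of months 1 to 2.

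**2. OS when lost patients differ in risk**

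Let h be the death hazard while followed, k × h the hazard after loss, and d the share lost before death. The loss rate is g = h × d/(1 − d).

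- True survival: S(t) = e^(−(h+g)t) + [g/((h+g) − kh)] × [e^(−kht) − e^(−(h+g)t)].
- Kaplan-Meier with losses censored estimates e^(−ht), so its median is ln 2/h.
- h is set so that the true median is 7.7 months. Example, k = 2 and d = 20%: h = 0.0846 per month, so the Kaplan-Meier median is 0.693/0.0846 = 8.2 months.

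| Risk after loss (k) | 10% lost | 20% lost | 30% lost |
|---|---|---|---|
| 0.5 | 7.5 | 7.3 | 7.1 |
| 1 | 7.7 | 7.7 | 7.7 |
| 2 | 7.9 | 8.2 | 8.5 |
| 4 | 8.2 | 8.7 | 9.4 |
| Death at moment of loss: 7.7/(1 − d) | 8.6 | 9.6 | 11.0 |

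Entries are Kaplan-Meier medians in months. For k = 2 to 4, OS is overstated by about 1 to 5 percentage points at 6 months and 1.5 to 9 points at 12 months.

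The exponential form is only a device. It implies 2-year OS of 0.5^(24/7.7) = 11.5%, against the 23% quoted in Protocol Section 7.

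**3. Time to CR/CRi**

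Take the same 6 of 32 non-responders, censored at 1-2 months, and assume that responses continue to 2.5 months. After 2 months only future responders are at risk, so the Kaplan-Meier cumulative probability of CR/CRi rises to 100%. The true proportion is 26/32 = 81%.

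**4. Scale against sampling error**

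With 6-month OS of 0.5^(6/7.7) = 58.3% and n = 32, the 95% half-width is 1.96 × √(0.583 × 0.417/32) = 17 points.

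**The case against.** **A reader might infer that Section 9.7 contradicts the RFS definition.** It does not. Censoring applies only where time-to-event information is unavailable. A charted and dated progression, relapse, discontinuation for deterioration or new induction is still an event under Section 3. Loss for an AE, and lack of efficacy without documented progression, are not listed RFS events. What remains is an overlap without a precedence rule for ambiguous charts. The RFS table above therefore shows what inconsistent coding could do, not what the plan prescribes.

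**A reader might infer that OS and RFS are biased upward.** The documents cannot establish that. They give neither the share lost nor the risk afterwards. Some losses will be for neutral reasons, and a patient lost after an AE may be in remission. At equal risk there is no bias, and at lower risk it reverses.

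**The effect is modest and the study is descriptive.** No hypothesis is tested (SAP 3.1), interpretation is to be qualitative (SAP 7.2), attrition is disclosed as a limitation, and OS and RFS are two of twelve unranked secondary endpoints. A bias of 1 to 5 points at 6 months is well inside a 17-point half-width. All of this is fair and limits the severity. It does not make the sentence in 9.7 correct, and a confidence interval does not reveal a systematic shift.

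**Counting every such loss as a death is extreme.** Agreed, so it belongs only in a sensitivity analysis.

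**Conclusion.** The point holds in limited form. Protocol 9.7 attributes to Kaplan-Meier a property that it has only under non-informative censoring, and the reasons for loss that it names make that assumption doubtful. Nothing in the SAP repairs this. OS, RFS and the cumulative probability of CR/CRi are likely overstated; this is not certain.

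Under the assumptions above, 6-month RFS could read up to about 10 points too high (39% to 49%) if all six assumed non-responders were coded as censored. Median OS could read about 0.2 to 1.7 months too high if 10-30% are lost at 2-4 times the risk. Both ranges rest on assumed inputs. The missing precedence rule and the lack of any sensitivity analysis or tabulation by reason are shown by the documents alone.

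**What to change.** - **Protocol 9.7:** replace the claim about attrition with a statement that Kaplan-Meier assumes censoring unrelated to prognosis, and that this may fail for losses due to AEs or lack of efficacy. SAP 7.1 contains no such claim, so nothing needs deleting there.
- **SAP 7.1/7.2, RFS:** state that any documented Section 3 event (death, progression, relapse, discontinuation for global deterioration, new induction, or HSCT without CR/CRi) takes precedence over censoring. Date it at its record or, failing that, at last contact.
- **OS:** keep censoring at last contact as the main analysis.
- **Sensitivity, OS and RFS:** add one analysis that counts losses for AE or lack of efficacy as events at last contact.
- **Sensitivity, time to CR/CRi:** add one analysis that keeps patients lost for lack of efficacy in the denominator as non-responders.
- **Reporting:** tabulate losses to follow-up by recorded reason.

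The cost is some SAP wording, one table and a few extra runs on data already being abstracted, provided that the CRF records the reason for loss and the date of last contact. RFS may look slightly less favourable.

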# 5.1 EFFICACY/EFFECTIVENESS ENDPOINT(S)

The primary outcomes of interest are CR/CRi achieved or not following InO treatment which will be measured by binary response and duration of remission which will be measured by time to achieve CR/Cri from InO therapy starts. Other secondary outcomes will be measured by binary response mostly, but time to event for dealth and relapse will be measured by time from starting of the therapy to the event of interest. The longest time from initiation of InO to date of data extracted will be considered as study period. The number of salvage therapies received prior to the InO therapy initiation will be classified into 0, 1 and >1.

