# 7.2 STATISTICAL ANALYSES

The distribution demographics variables like age and sex will be summarized by mean  $\pm$ SD and frequency (%) respectively. The prevalence of complete remission or complete remission with incomplete hematological recovery following treatment with InO will be reported with 95% confidence interval. Further these prevalence will be estimated for the

number of salvage therapies  $(0, 1, \ge 2)$  received before InO initiation.6 months or 12 months restricted mean remission free time will be estimated with 95% CI for both complete remission or complete remission with incomplete hematological recovery. The Kaplan-Meier curves of remission free survival will be drawn if a sufficient representation observed across the number of salvage therapies  $(0, 1, \ge 2)$  received before InO initiation. The restricted mean remission free time with 95% CI will be estimated for categories of number of salvage therapies. Restricted mean/median survival time will also be estimated with 95% CI. The Kaplan-Meier overall survival curve will also be drawn.

Other secondary endpoints like MRD negativity following initiation of InO or dosage pattern, concomitant medications, cause of death , occurrence of Grade 3/4 treatment-related adverse events in lung/cardiac/kidney/liver etc. following InO initiation and CR/CRi in EMD/LBL will also summarized by frequency and percentage and dration of response(DOR), no of patients who proceeded to transplant, total during study treatment and post HSCT will be summarized my median and interquartile range. restricted relapse-free-survival time will also be estimated with 95% CI if data permits for all patients and patients with or without follow-up HSCT.

Due to non-probability sampling technique, the extrapolation of the results will be restricted to the population that matches with sample characteristics only. Magnitude of the measure of any characteristics will be prioritised over statistical interpretation. However, interpretation of the result will be in a qualitative sense even though the related feature is compared numerically owing to descriptive nature of the study.

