# 7.2.2 Analyses of endpoint

The following tables and figures will be generated for the analysis of endpoints.

- 1. The distribution of demographics characteristics (mean ±SD for age and frequency and percentage for sex)
- 2. MRD negativity following initiation of InO (frequency and percentage)
- 3. Dosage pattern (frequency and percentage)
- 4. Cause of death (frequency and percentage)
- 5. Occurrence of Grade 3/4 treatment-related adverse events in lung/cardiac/kidney/liver etcfollowing InO initiation (frequency and percentage)
- 6. CR/CRi in EMD/LBL (frequency and percentage)
- 7. Duration of response (DOR) (Median and Interquartile Range (IQR))
- 8. No of patients who proceeded to transplant (Median and IQR)
- 9. Total during study treatment and post HSCT (Median and IQR)
- 10. Restricted remission free time with 95% confidence interval for both complete remission and complete remission with incomplete hematological recovery.

- 11. Restricted remission free time with 95% confidence interval for both complete remission and complete remission with incomplete hematological recovery stratified by the number of salvage therapies  $(0, 1, \ge 2)$  received before InO initiation
- 12. Restricted mean overall survival time with 95% CI.
- 13. Restricted relapse-free-survival with 95% CI for all patients and patients with or without follow-up HSCT.

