#### List of figure

- 1. Kaplan-Meier curve for remission free survival
- 2. Kaplan-Meier curve for remission free survival stratified by the number of salvage therapies (0, 1, ≥2) received before InO initiation
- 3. Kaplan-Meier survival curve for overall survival

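### SAP 5.1 measures duration of remission as time to remission, and the planned time-to-CR/CRi analyses have no rule for death, new induction or HSCT without remission

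*Protocol*

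**What the plan says.** **Definition.** SAP 5.1 names as a primary outcome, beside CR/CRi achieved or not, "duration of remission which will be measured by time to achieve CR/Cri from InO therapy starts". Protocol 9.1.3 and the primary endpoint in SAP section 5 declare only CR/CRi by number of prior salvage therapies. Both secondary endpoint lists contain DOR and the number of cycles needed to attain CR/CRi; neither contains time to CR/CRi. Protocol section 3 does not define DOR, and SAP Appendix A1.2 adds no endpoint definitions.

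**Analysis.** For patients marked as censored, Protocol 9.7 states that "the use of Kaplan-Meier curves will be obtained as estimates of median OS, RFS and time to CR/Cri taking into account" attrition. Its examples of loss to follow-up include adverse events and lack of efficacy. It censors when time to event is unknown "due to loss to follow-up or non-occurrence of outcome events before the end of the study". SAP 7.2 plans, at 6 or 12 months, "restricted mean remission free time will be estimated with 95% CI for both complete remission or complete remission with incomplete hematological recovery", and adds: "The restricted mean remission free time with 95% CI will be estimated for categories of number of salvage therapies". Tables 10 and 11 in SAP 7.2.2 carry this through, Table 10 as "Restricted remission free time with 95% confidence interval for both complete remission and complete remission with incomplete hematological recovery". Figure 1 is a "Kaplan-Meier curve for remission free survival", and Figure 2 is the same by number of prior salvage therapies.

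**Exits without remission.** Death, and new induction or HSCT without CR/CRi, are dealt with only in the RFS definition in Protocol section 3, where they count as events.

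**The concern.** There are two separate problems.

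First, SAP 5.1 is the only place in either document that says how duration of remission is measured, and it describes a different interval: index date to remission, not remission to its end. Programmed as written, Table 7 (DOR) would report how fast patients remit, not how long remission lasts. The same sentence gives primary status to something that the endpoint lists make secondary or do not list at all.

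Second, a patient who dies without remission can no longer remit, and one who starts new induction or goes to HSCT can no longer remit on InO alone. If such patients are censored on leaving, Kaplan-Meier treats them as still able to remit at the rate of those who remain. One minus Kaplan-Meier (1−KM) then exceeds the share who actually remit, and the restricted mean is shortened. The report could show a remission curve above its own CR/CRi proportion. Table 11 could also show a gap between salvage strata that comes only from when non-remitters left.

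**Working it through.** The plan gives no expected remission curve or exit times, so there is no figure to reproduce. The check is illustrative.

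**Inputs.** N = 32 (administrative change letter, item 4; the SAP still says about 55). Remissions: 26 of 32 = 81.25%, close to the 81% cited for InO in Protocol section 7. Assumed: remissions 9, 9 and 8 at months 1, 2 and 3, and six patients leaving without remission. Assumed exits fall at 1.5 months or later, because Protocol 9.1.2 excludes patients without one completed cycle; cycle length is not in the documents. Exits not counted as early are at 3.5 months. Curves are carried flat to 12 months.

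**Formulas.** Kaplan-Meier with exits censored at exit: S(t) = ∏(1 − d/n). Aalen-Johansen: CIF(t) = Σ A·d/n, where A is the proportion with neither remission nor exit just before each remission time. Restricted mean = area under S, or under 1 − CIF, to 12 months.

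**No early exit.** S = 23/32, 14/32, 6/32. 1−KM = 26/32 = 81.25%. Restricted mean = 1 + 23/32 + 14/32 + 9 × 6/32 = 3.84 months.

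**One exit at 1.5 months.** S at month 2 = (23/32)(13/22) = 0.4247; at month 3, × 5/13 = 0.1634. 1−KM = 83.7%. Restricted mean = 1 + 0.7188 + 0.4247 + 9 × 0.1634 = 3.61.

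**Exits at 1.5 and 2.5 months.** S at month 3 = 0.4247 × 4/12 = 0.1416. 1−KM = 85.8%. Restricted mean = 1 + 0.7188 + 0.4247 + 9 × 0.1416 = 3.42.

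**Aalen-Johansen, same two exits.** 9/32 + (22/32)(9/22) + (12/32)(8/12) = 26/32 = 81.25%; the area is 3.84. It is the same for every exit pattern.

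| Early exits (of 6) | 1−KM | Restricted mean (months) | Median (months) |
|---|---|---|---|
| 0 | 81.25% | 3.84 | 2 |
| 1 | 83.7% | 3.61 | 2 |
| 2 | 85.8% | 3.42 | 2 |
| 4 (2 + 2) | 91.8% | 2.87 | 2 |
| 6 (3 + 3) | 100% | 2.11 | 2 |

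With a 6-month horizon the multiplier 9 becomes 3, and the first three restricted means are 2.72, 2.63 and 2.57 months.

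**Lower remission rate (assumed 21/32, as 7/7/7).** With 0, 2 or 4 early exits of 11, 1−KM is 65.6%, 68.9% or 72.8% and the restricted mean 5.44, 5.14 or 4.77 months. The extreme, all 11 early, is 100% and 2.29 months. The median is 3 months throughout.

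**One salvage stratum (assumed n = 11, remissions 3/3/3, two exits).** Both late: 81.8%, 3.82 months. One at 1.5 months: S = (8/11)(4/7)(1/4) = 0.104, so 89.6% and 3.08 months. Both early: 100%, 2.14 months. Identical remissions at identical times could thus differ in Table 11 by 3.82 − 3.08 = 0.74 to 3.82 − 2.14 = 1.68 months.

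**Exits kept at risk as non-remitters to the horizon.** In the 26-remission example S is again 23/32, 14/32, 6/32, so there is no bias.

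**The case against.** The strongest reply is that the plan does not adopt censoring at exit. A patient known to have died or switched without CR/CRi is not lost to follow-up. Such a patient fits the clause on non-occurrence before the end of the study, and SAP 5.1 says: "The longest time from initiation of InO to date of data extracted will be considered as study period". On that reading these patients stay in the risk set and nothing is biased. This stands as a possible reading. It does not settle the matter, because Protocol 9.7 offers Kaplan-Meier for patients lost through adverse events or lack of efficacy and gives no censoring date.

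Other replies also stand in part:

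- Protocol 9.7 asks for a median, and the median does not move in any example above. The coarse monthly grid helps to hold it fixed.
- Figures 1 and 2 may be a slip for relapse-free survival. SAP 7.1 promises a relapse-free survival curve, the figure list has none, and RFS already counts these exits as events. Tables 10 and 11 cannot be explained this way, because they name CR and CRi and Table 13 covers relapse-free survival.
- The 3.84-month reference counts time after death as time without remission. That is a choice of estimand and should be stated as one.
- The study is descriptive, and SAP 7.2 calls for qualitative interpretation. It makes the stratified curves conditional on sufficient representation, and SAP 4.4 limits subgroup analyses to what the data permit. The sentence on stratified restricted means carries no such condition.

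None of these replies touches the wording of SAP 5.1 on duration of remission.

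**Conclusion.** The definition in SAP 5.1 is wrong as written and conflicts with the endpoint lists. That part needs no assumption.

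The missing rule for exits is a real gap with a conditional consequence. If exits are censored at exit, the direction is certain whenever a remission follows an exit. The size rests on exit times that the documents do not give. One or two early exits of six add 2.4 to 4.6 percentage points (83.7 or 85.8 less 81.25) and take 0.23 to 0.42 months off the 12-month restricted mean (3.84 less 3.61 or 3.42). This is small beside the exact 95% interval for 26/32, 64% to 93%. Larger shifts need most non-remitters to leave before the last remission.

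A reader might infer that the primary result is biased, or that the plan commits to the biased method. The documents support neither: the CR/CRi proportion is a separate estimate with its own interval, and the censoring text allows an unbiased reading. Nor does the sentence in SAP 5.1 make duration of remission a declared primary endpoint. Severity is minor to moderate, limited to secondary displays.

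**What to change.** 1. In SAP 5.1, rename the variable time to first CR/CRi and remove it from the primary outcomes. Measure DOR from first CR/CRi to relapse or death, and use that in Table 7.
2. In SAP 7.2 and Tables 10 and 11, treat CR/CRi as one combined event. Estimate time to first CR/CRi by Aalen-Johansen cumulative incidence at 6 and 12 months with 95% CI. Death, and new induction or HSCT without CR/CRi, are competing events; censor only at last contact or data extraction. When follow-up is complete, keeping these patients at risk as non-remitters to the horizon is equivalent. Align Protocol 9.7.
3. If a restricted mean is kept as the area under 1 − CIF, state that it counts time after an exit as time without remission.
4. Report by salvage stratum only where numbers permit.
5. State whether Figures 1 and 2 show time to remission or relapse-free survival, and list the relapse-free survival curve promised in SAP 7.1.

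The cost is SAP wording and a standard software routine. No new data are needed, because the dates of these exits are already required for RFS. The remission curve may look less favourable, and estimates stay imprecise: the exact 95% interval for 9/11 in a stratum is 48% to 98%. The method does not repair true loss to follow-up related to lack of efficacy, so the number of such patients should be reported.
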